17 APPENDICES

Appendix 1: Case Report Forms

Appendix 2: Mixed-methods operational research tools

Appendix 3: Informed Consents

### Revision history

Protocol version	SAP version no.	Section number changed	Description of and reason for change	Date changed
v5.0	v1.2	3.4	Re-calculation of sample size due to lower than expected recruitment	7 September 2022

# 1. Abbreviations and glossary of terms

CDSA	Clinical Decision Support Algorithm
CI	Confidence interval
CRP	C-reactive protein
ePOCT+	Name of CDSA (not an abbreviation)
HIV	Human Immunodeficiency Virus
HF	Health facility
HCW	Health care worker
IHI	Ifakara Health Institute
IQR	Interquartile range
IMCI	Integrated management of childhood illness
NCD	Non-communicable disease
NIMR	National Institute of Medical Research
PCs	Personal Computers
PHC	Primary health care
POC	Point-of-care
PRECIS-2	Pragmatic Explanatory Continuum Indicator Summary 2
RDT	Rapid Diagnostic Test
Swiss TPH	Swiss Tropical and Public Health Institute
TZ	Tanzania
TB	Tuberculosis
Unisanté	Centre for Primary Care and Public Health (University of Lausanne)
WHO	World Health Organization

## 2. Introduction

### 2.1 Hypothesis

Hypothesis: In routine conditions, Health Care Workers (HCWs) provided with an electronic clinical decision support algorithm (CDSA) on tablets or PCs can treat sick children attending primary health care facilities in Tanzania with appropriate antimicrobial prescriptions while maintaining a good clinical outcome.

Research hypothesis: The use of ePOCT+ for case management of sick children in primary care health facilities, compared to routine care, are prescribed less antibiotics at the initial consultation, and have the same proportion of cure rates at day 7 after their initial consultation.

### 2.2 Objective

Overall project objective: Improve the **integrated management of children with an acute illness** through the provision of an electronic CDSA (ePOCT+) to clinicians working at primary care level.

Objective of Phase 1 study:

The primary objective of this trial is to determine if the use of ePOCT+ for case management of sick children in primary care, compared to routine care:

- (i) results in less antibiotic prescriptions at initial consultation;
- (ii) is non-inferior in clinical outcomes at day 7.

[figure not shown]
## 3. Methods

### 3.1 Study design

[figure not shown]
The DYNAMIC TZ Phase 1 study is a pragmatic, open-label cluster randomized controlled study. The intervention evaluated consists of the provision to health workers the ePOCT+ clinical decision support algorithm (CDSA) displayed on tablets (medAL-reader), point-of-care tests proposed by ePOCT+ that are not part of routine care (pulse oximeter, CRP rapid test, additional hemoglobin cuvettes), complementary training on the tool, regular monitoring and mentorship/supervision visits by the study team and/or the Council Health Management Team (CHMT). Mentorship and supervision will be enabled by a complementary dashboard (medAL-monitor), used to visualize and monitor study-related indicators. Due to the pragmatic nature of the study, the design is adaptive, in that changes in the implementation throughout Phase 1 may be made based on monitoring data and feedback from the health facilities. These implementation changes (excluding significant adaptations to algorithm content) will be thoroughly documented and accounted for in longitudinal analyses.

Since the intervention takes place at the health provider level and their practices are influenced by the context of the health facility they are working in, randomization at health facility level rather than at HCW level or at individual patient level was chosen. The randomization of clusters (i.e. health facilities) will be performed on a 1:1 ratio. Thus, ePOCT+ will be provided to health care workers of 20 of the 40 selected primary health care facilities (intervention arm) in the Morogoro and Mbeya regions, while the other 20 health facilities (HFs) will serve as controls (control arm). Sick children aged 1 day to 14 years (inclusive) will be managed in accordance with the study arm to which the HF they attend has been assigned. The comparator for Phase 1 will be routine care as currently implemented in Tanzania supplemented with equivalent clinical training given to the intervention arm. This includes routine clinical supervision visits performed by CHMT members. To assess the primary and secondary outcomes, final decision on referral, laboratory test results, diagnoses and treatments at initial consultation will be recorded by HCWs electronically in both arms (in the intervention arm integrated into the CDSA; in the control arm via a simple eCRF without any decision support); children will also be followed-up by a phone call or home visit to their caregiver at day 7 (range 6-14) to determine their clinical status. The study is considered as pragmatic since there are no major exclusion criteria to the population of interest, and the setting and organization of the health facilities remains mostly the same (see PRECIS-2 wheel below).

The trial design is summarized below:

PRECIS-2 (Pragmatic-Explanatory Continuum Indicator Summary 2) wheel summarizing the extent of pragmatism of the study:

## 3.2 Randomization

The 40 health facilities to be included in the study will be randomly selected from all eligible health facilities in the participating councils (Mlimba district council, Ulanga district council, Ifakara town council, Mbeya district council, and Mbeya city council). Eligible health facilities include public health centers and dispensaries with at least 20 consultations with children between 2 months and 5 years of age per week. Cluster inclusion and exclusion criteria will first be applied to the full list of health facilities in the participating councils prior to selection and randomization. The random selection will follow a 3:2 ratio of health facilities between Morogoro and Mbeya regions, respectively, and include exactly 4 health centers per region.

Health facilities (or clusters) will be randomized (1:1), to using ePOCT+ (intervention) or routine care (control group). Randomization will be stratified by council, type of health facility (health center versus dispensary), and attendance rate. An independent statistician will perform both the sampling and randomization.

## 3.3 Sample size

The primary analysis will evaluate whether the use of ePOCT+ for case management of sick children in PHC facilities 1) results in similar clinical cure at day 7 (non-inferiority analysis), as compared to routine care and 2) decreased antibiotic prescriptions (superiority analysis) at the initial consultation. The sample size was calculated for testing the non-inferiority of the clinical cure outcome, which will require a much larger sample size due to the rareness of clinical failure. In addition, the testing of differences in antibiotic prescription is conditional on satisfying non-inferiority in the clinical outcome. Assuming a failure rate (not being cured at day 7) of 3% in the control arm (corresponding to a 97% clinical cure rate), based on previous studies, the acceptable non-inferiority margin will be a risk ratio of 1.3. This corresponds to the upper bound of the difference in failure rate not exceeding 0.9% if the control group failure rate is 3%. We utilized a fixed risk ratio rather than an absolute risk difference to protect against potential unexpected event rates (Head et al. 2012).

We assumed a cluster size of 900 patients (average of 150 patients per month x 6 months) and an intraclass correlation coefficient of 0.002 in the clinical outcome based on similar studies. To have 80% power to detect a risk ratio 1.3, for a one-sided hypothesis test at alpha of 0.025, we would require 19 clusters and 17,100 patients per arm (total patients n=37,620 assuming 10% loss to follow-up), rounded to a total of 40 HFs and 40,000 patients. However, due to uncertainty regarding the assumptions of the sample size calculation and to capture a wider more representative range of conditions, we will continue recruitment for Phase 1 for a minimum of 6 months.

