## 3.4 Statistical Interim analyses

No formal interim analysis was planned for the primary endpoints. However due to lower enrollment than expected after 8 months of recruitment, we planned an ad-hoc sample size recalculation to calculate the expected power of the study based on updated parameters. The power will be re-calculated using the actual clinical failure data from the control arm, adjusting the upper limit of the non-inferiority margin based on the risk ratio of 1.3, and taking into the actual enrollment numbers extrapolated up to mid-October 2022 (which corresponds to the end of 6 months of enrollment in all health facilities). All the other sample size calculation parameters will remain the same (see above)). The following approaches will therefore be undertaken based on the calculated power:

- If the updated sample size calculation finds a power of  $\geq 80\%$ , then the study will end as planned mid-October 2022.
- If the updated sample size calculation finds a power of  $< 80\%$  we will prolong the study, or increase the number of health facilities as required.

The sample size recalculation will be performed by an independent statistician, who will share the results of the updated sample size to the study investigators. To avoid implementation bias, the clinical failure proportion in the control arm will not be shared.

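### The sample size and the mid-trial power recalculation have no term for unequal facility sizes, so the power compared with the 80% stop/prolong threshold is somewhat too high

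*SAP*

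**What the plan says.** SAP 3.3 (and Protocol 10.1.1, which uses the same figures) takes a single cluster size: "We assumed a cluster size of 900 patients (average of 150 patients per month x 6 months"), with "an intraclass correlation coefficient of 0.002 in the clinical outcome based on similar studies". The target is stated as "To have 80% power to detect a risk ratio 1.3, for a one-sided hypothesis test at alpha of 0.025", and the result is "we would require 19 clusters and 17,100 patients per arm (total patients n=37,620 assuming 10% loss to follow-up), rounded to a total of 40 HFs". Neither document gives a standard deviation, a CV or any inflation for unequal facilities.

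Other parts of the SAP bear on whether facilities are alike:

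- Section 3.2 selects 40 facilities with exactly 4 health centres in each of two regions, which makes 8 health centres and 32 dispensaries. It adds: "Randomization will be stratified by council, type of health facility (health center versus dispensary), and attendance rate".
- Section 5.2.1 sets a minimum weekly attendance and no upper limit.
- Section 3.4 describes 8 months of recruitment already completed, yet gives mid-October 2022 as the date when every facility will have reached 6 months. Facilities therefore started at different times.

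Section 3.4 then sets a decision rule. Power is recalculated from the control-arm failure rate, the margin re-expressed from the risk ratio of 1.3, and actual enrolment extrapolated to mid-October. For the rest: "All the other sample size calculation parameters will remain the same". At 80% or more recruitment ends; below 80% the study is prolonged or facilities are added.

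**The concern.** The usual design effect, 1 + (m − 1) × ICC, is right when every cluster has m children. When sizes vary around a mean of m, the same total number of children carries less information, because large facilities add many correlated observations. Stratifying by attendance balances the arms but does not recover that loss.

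This matters most in SAP 3.4, because there the power figure triggers an action. If the equal-size formula returns just over 80%, recruitment stops, although the true figure may be below the SAP's own threshold. Non-inferiority on clinical failure also comes first in the testing sequence, so a shortfall there also lowers the chance of reaching the test of antibiotic prescription. By the time of the recalculation, facility enrolment counts exist and can replace the assumption.

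**Working it through.** **Inputs from SAP 3.3.** Control failure 3%; margin 0.009 (risk ratio 1.3 at 3%); one-sided alpha 0.025 (z = 1.960); power 80% (z = 0.842); m = 900; ICC 0.002. I read 900 as children with a day-7 outcome, because 19 × 900 = 17,100 comes before the 10% loss inflation.

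**1. The plan's own figure.**
- Without clustering: (1.960 + 0.842)² × 2 × 0.03 × 0.97 / 0.009² = 5,640 per arm.
- Equal-size design effect: 1 + 899 × 0.002 = 2.798.
- 5,640 × 2.798 = 15,781 per arm; divided by 900, 17.5 clusters. Adding one cluster, as the standard cluster-count formula does, gives 18.5, rounded up to 19.
- 19 × 900 = 17,100; 2 × 17,100 × 1.10 = 37,620.

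Both stated totals are reproduced exactly. The calculation contains no allowance for unequal sizes.

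**2. How unequal might facilities be?** The documents give no CV. As an illustration from facility type alone, with 8 health centres and 32 dispensaries, the CV is 0.33, 0.57 or 0.75 if a health centre enrols 2, 3 or 4 times as many children as a dispensary. I use 0.3 to 0.7 as an assumed range.

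**3. What a recalculated 80% means.** Two versions:
- *Standard formula:* DE(CV) = 1 + ((1 + CV²) × m − 1) × ICC. Relative efficiency RE = 2.798 / DE(CV).
- *Efficient weighting:* RE = mean of x / (1 + (x − 1) × ICC) over facility sizes x, divided by 900 / 2.798. Sizes are assumed gamma-distributed with mean 900. This is closer to the random-effects logistic model in SAP 6.2.

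True power = Φ(2.802 × √RE − 1.960). Example, CV 0.5, standard formula: RE = 2.798 / 3.248 = 0.861; 2.802 × 0.928 − 1.960 = 0.640; power 73.9%.

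| CV | DE(CV) | Standard: RE | Power | Efficient: RE | Power |
|---|---|---|---|---|---|
| 0 | 2.798 | 1 | 80.0% | 1 | 80.0% |
| 0.3 | 2.960 | 0.945 | 77.8% | 0.979 | 79.2% |
| 0.5 | 3.248 | 0.861 | 73.9% | 0.944 | 77.7% |
| 0.7 | 3.680 | 0.760 | 68.5% | 0.895 | 75.5% |

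With a mean of 600 the results barely change: 78.1%, 74.8% and 70.1% (standard); 79.1%, 77.6% and 75.4% (efficient).

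**4. Planned power at 20 × 900 per arm.** SE = √(2 × 0.03 × 0.97 / 18,000 × 2.798) = 0.00301; 0.009 / SE = 2.992; 2.992 − 1.960 = 1.032; power 84.9% with equal sizes. At CV 0.3, 0.5 and 0.7 it is 82.9%, 79.3% and 74.2% (standard), or 84.2%, 82.8% and 80.8% (efficient). It drops below 80% from a CV of about 0.47 (standard) or nearly 0.8 (efficient). These are normal approximations. A t-based version gives 83.0% at CV 0, and a similar one-cluster correction at CV 0.7 with efficient weighting gives Φ(2.992 × √0.895 × √(19/20) − 1.960) = 78.8%, so the top of the range is marginal.

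**5. Where the threshold lies.** At 3% failure and 20 facilities per arm, the equal-size formula crosses 80% near 650 children per facility: DE = 1 + 649 × 0.002 = 2.298; SE = √(0.0582 / 13,000 × 2.298) = 0.00321; power 80.1%. With enrolment already reported below expectation, a result close to 80% is a realistic case.

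**The case against.** A reader might infer from "All the other sample size calculation parameters will remain the same" that the recalculation keeps 900 children per facility and overstates power for that reason. The documents do not support this. Enrolment is one of the named updates, so the mean size is probably revised. Keeping 900 in the design effect while enrolment fell would bias the result the other way: at 600 per facility, 20 per arm and 3% failure, power is 68.6% with the 900-based design effect and 78.7% with the actual mean.

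A reader might also infer that the planned design falls short of 80%, or that SAP 3.3 contains an arithmetic error. Neither is shown. The stated totals reproduce exactly. The plan has 20 facilities per arm where 19 were required, and with efficient weighting the normal approximation keeps it above 80% throughout the assumed range. SAP 3.3 also acknowledges uncertainty in its assumptions and sets a minimum recruitment period. Power on a log risk-ratio scale is lower, but already so with equal facilities; that is a separate question.

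The standard formula is pessimistic for this trial, because a random-effects model weights facilities more efficiently. It is best read as an upper bound on the loss. The reference to actual enrolment could also be taken to mean facility-by-facility counts, but nothing in SAP 3.4 says so, and no measure of spread is named.

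What remains is that, for any CV above zero, an equal-size calculation returns too high a power, and a stop/prolong decision depends on it.

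**Conclusion.** The point holds in limited form. SAP 3.3 assumes equal facilities, other sections of the SAP imply that they are not, and SAP 3.4 applies an 80% rule with no term for the difference. The direction is certain for any CV above zero; the size is not, because no CV is given.

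Over an assumed CV of 0.3 to 0.7 with a mean of 900, a recalculated 80% overstates power by about 2 to 11 percentage points by the standard formula, and by about 1 to 4.5 points with efficient weighting. The second range is the better guide to the planned analysis. It rests on gamma-distributed sizes, an ICC of 0.002 and a normal approximation. A recalculated power well above 80% would probably lead to the same decision either way; the risk lies in a result at or just above the threshold.

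**What to change.** In SAP 3.4, state that the independent statistician will compute power from facility-level enrolment, observed and extrapolated to mid-October 2022. Either the actual sizes or their mean and CV should enter the design effect before the 80% rule is applied. State which formula is used (standard or efficient weighting), and report the CV with the result.

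The cost is small. The enrolment counts already exist, and facility sizes reveal nothing about outcomes, so the control-arm failure proportion can still be withheld as planned. The margin, alpha and analysis model do not change. The drawback is a slightly less favourable power figure, which could lead to prolonging the study when the equal-size formula would have ended it.

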	which will require a much larger sample size due to the rareness of the event. In addition, the testing of differences in antibiotic prescription is conditional on satisfying non-inferiority in the clinical outcome. Assuming a cure rate of 97% in the control arm based on previous studies, the acceptable absolute non-inferiority margin will thus be one third of 3% (100%-97%), thus 1%. We assumed a cluster size of 900 patients and an intraclass correlation coefficient of 0.002 in the clinical outcome based on similar studies. To have 80% power to detect this difference of ≥1%, for a one-sided hypothesis test at alpha of 0.025, we would require 19 clusters and 17,100 patients per arm (total patients n=37,620 assuming 10% loss to follow-up), rounded to a total of 40 HFs and 40'000 patients. For Phase 2, sample sizes for the randomized sub-studies, aimed at evaluating the effect of a modification in the algorithm leading to a potential positive impact, will be calculated following the same general principles. In Phase 2, we expect that an average of 200 children per month per HF will be managed using ePOCT+, which corresponds to around 500,000 consultations over 2 years in the 100 HFs selected on predefined criteria.
Study duration	Phase 1 (including pilot phase): January 2021 – March 2022 Phase 2: April 2022 – October 2023 Implementation research: January 2021 – January 2023 Sustainability assessment: January 2023 – March 2024 Diseases Surveillance: October 2021 – March 2023
Study schedule	Cluster-randomized controlled study data collection (Phase 1): Sep 2021 – Mar 2022 Data collection for the evaluation of the spatiotemporal/prognostic adaptations of ePOCT+ (Phase 2): Apr 2022 – Oct 2023
	Data collection for the evaluation of the smart disease surveillance and outbreak detection system: Oct 2021 – Mar 2023
	Data collection for the cross-sectional mixed-methods studies: Jan – Mar 2021; Jan – Mar 2022; Jan – Mar 2023
	Final data analysis of phase 2 and of the contextual evidence that drives sustainability and future scale up: Jan 2023 – Mar 2024
Ethical statement	The research project will be carried out in accordance with the research plan outlined in this protocol and with principles enunciated in the current version of the Declaration of Helsinki, Essentials of Good Epidemiological Practice issued by Public Health Switzerland (EGEP) as well as all national legal and regulatory requirements as applicable.

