Analyses will follow CONSORT guidelines (Schulz et al. 2010, Piaggio et al. 2012) and intention-totreat (ITT) principles, that is including all participants as randomized. A flowchart will describe the inclusion and follow-up of participants by study arm. Baseline characteristics will be described by study arm with summary statistics such as median and interquartile range or number and percentage; no formal testing between arms will be performed (Pocock et al. 2002). Outcomes will be described by arm using summary statistics. For the non-inferiority comparison between ePOCT+ and the control arm for clinical cure, a CI approach will be used. A figure illustrating the CIs and the non-inferiority margin will be presented. Primary analyses for the non-inferiority comparison will be performed on both the per protocol and ITT sets (Committee for Proprietary Medicinal P 2001). If ePOCT+ is found to be non-inferior to the control in terms of clinical cure rate, then we will assess for superiority using the ITT set. If non-inferiority is established, we will test for significant differences in the co-primary outcome of antibiotic prescription rate. For this outcome, the percentage of patients receiving antibiotics at day 0 will be assessed using multi-level logistic regression model regression with the cluster included as a random effect. Binary secondary outcomes will be evaluated in the same way. All estimates will be reported with 95% confidence intervals (CI).

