## 6.2 Analysis methods

Analyses will follow CONSORT guidelines (Campbell, Piaggio, Elbourne, & Altman, 2012; Piaggio et al., 2012; Schulz, Altman, & Moher, 2010; Zwarenstein et al., 2008). Outcomes will be described by arm using summary statistics. For the non-inferiority comparison between ePOCT+ and the control arm for clinical failure, a CI approach will be used using a random effects logistic regression model using the cluster (health facility) and patient as random effects. A figure illustrating the 95% CIs of the ITT and PP relative risk of clinical failure will be presented with the pre-specified non-inferiority margin of 1.3. Non-inferiority will be achieved if the upper-bound of the RR does not surpass 1.3. If ePOCT+ is found to be

non-inferior to the control in terms of clinical failure using the PP population, then we will assess for superiority using the ITT population. Superiority will be achieved if the relative risk CI of the ITT set does not surpass 1. If clinical failure non-inferiority is established, we will test for significant differences in the co-primary outcome of antibiotic prescription rate. Since the documentation of the final treatment in both arms is part of the per protocol definition, only the PP population can be used. For this outcome, the percentage of patients receiving antibiotics at the initial consultation will also be assessed using a random effects logistic regression model with the cluster (health facility) and patient included as random effects. Binary secondary outcomes and additional analyses will be evaluated in the same way. All estimates will be reported with two-sided 95% confidence intervals (CI), except for the non-inferiority analysis which will be reported with one-sided 95% CI. The study will be deemed a success if clinical failure in the ePOCT+ arm is non-inferior to the control arm, and antibiotic prescription at the initial consultation is 25% less in the ePOCT+ arm compared to the control arm.

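### The stated 80% power does not hold for the risk-ratio test at one-sided alpha 0.025 (about 72–74% with 20 clusters per arm), and the SAP uses two different alphas for that test

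*SAP*

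**What the plan says.** **Sample size.** SAP 3.3 and protocol 10.1.1 give the same statement: "To have 80% power to detect a risk ratio 1.3, for a one-sided hypothesis test at alpha of 0.025, we would require 19 clusters", that is, 17,100 children per arm, rounded up to 40 facilities in all. The inputs are 3% failure in the control arm, 900 children per cluster and an ICC of 0.002. Both sections say the margin was fixed as a risk ratio and not as an absolute difference, and both translate it to 0.9 percentage points at 3% failure. Neither gives a formula.

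**Decision rule.** SAP 6.2 works on the ratio scale: "Non-inferiority will be achieved if the upper-bound of the RR does not surpass 1.3". It reports all estimates with two-sided 95% intervals, "except for the non-inferiority analysis which will be reported with one-sided 95% CI". Protocol 10.3 promises 95% intervals, without naming a side and without an exception for non-inferiority.

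**Recalculation.** Because enrolment was low, SAP 3.4 recomputes power from the observed control failure rate, "adjusting the upper limit of the non-inferiority margin based on the risk ratio of 1.3", and leaves the other parameters unchanged. At 80% or more the study ends in mid-October 2022. Below 80% it is prolonged or facilities are added.

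**Synopsis.** The protocol synopsis gives the same 19 clusters for a different margin: "the acceptable absolute non-inferiority margin will thus be one third of 3% (100%-97%), thus 1" percent.

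**The concern.** A margin of 1.3 on the risk ratio and a margin of 0.9 points on the difference describe the same boundary at 3% failure, but tests on the two scales do not have the same power. On the log scale the distance to the margin is log(1.3) = 0.262, against a relative distance of 0.30 on the difference scale. On the contrast p1 − 1.3·p0, the control-arm variance is multiplied by 1.3², so 2pq becomes 2.69pq. Either way the ratio test needs more clusters. A sample size that is right for the difference is therefore too small for the ratio at the same alpha.

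The alpha also changes between sections. SAP 3.3 sizes the trial at 0.025, while the one-sided 95% interval in SAP 6.2 is a test at 0.05.

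Two decisions depend on this. Non-inferiority gates the test of antibiotic prescription, so a shortfall in power puts both co-primary results at risk. SAP 3.4 also uses the power figure as its rule for ending or extending enrolment.

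**Working it through.** **Inputs.** From SAP 3.3: control failure p = 0.03, margin RR 1.3 (0.009 as a difference), m = 900, ICC 0.002, power 80%, one-sided alpha 0.025. From SAP 6.2: one-sided alpha 0.05. Assumed: true RR = 1, equal cluster sizes, no gain from stratification or covariate adjustment.

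**Step 1: design effect.** 1 + 899 × 0.002 = 2.798. Clusters per arm = n × 2.798 / 900, where n is the per-arm size under individual randomization.

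**Step 2: reproduce the 19.** At alpha 0.025, (1.960 + 0.842)² = 7.849. On the difference scale, n = 7.849 × 2 × 0.0291 / 0.009² = 5,640, which gives 17.53 clusters. Adding one cluster, as is common in cluster trials, gives 18.53, rounded up to 19.

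**Step 3: the test in SAP 6.2 at 0.025.**
- Log RR: 7.849 × 2 × (0.97/0.03) / 0.2624² × 2.798/900 = 22.92 clusters.
- Contrast p1 − 1.3·p0: 7.849 × 2.69 × 0.0291 / 0.009² × 2.798/900 = 23.58 clusters.

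**Step 4: the same at 0.05.** (1.645 + 0.842)² = 6.183. Log RR needs 18.06 clusters, which also rounds up to 19. The contrast needs 18.58 and the difference 13.81.

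**Step 5: power of the log-RR test.** Effective n = 900k/2.798 and SE = √(2 × 0.97/(0.03 × effective n)). For k = 20, effective n = 6,433, SE = 0.1003 and 0.2624/0.1003 = 2.617. Then 2.617 − 1.960 = 0.657 gives 74.4%, and 2.617 − 1.645 = 0.972 gives 83.4%.

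| Clusters per arm | alpha 0.025 (normal / t) | alpha 0.05 (normal / t) |
|---|---|---|
| 19 | 72.3% / 69.9% | 81.7% / 80.4% |
| 20 | 74.4% / 72.2% | 83.4% / 82.2% |

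For the contrast with 20 clusters at 0.025, power is 73.2% / 71.0%. For the difference it is 84.9% (normal). A beta-binomial simulation with 40,000 replicates agrees with the log-RR figures: about 74% / 72% at 0.025 and 83% / 82% at 0.05 with 20 clusters. With 24 clusters at 0.025 it gives 81.6% / 80.2%.

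**Step 6: the SAP 3.4 trigger.** Take 20 facilities per arm and 3% failure. With m evaluable children per facility, 80% power requires 20m/(0.998 + 0.002m) to equal the required n.

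| Scale and alpha | Required n per arm | m for 80% power |
|---|---|---|
| Difference, 0.025 | 5,640 | 645 |
| Log RR, 0.05 | 5,808 | 691 |
| Log RR, 0.025 | 7,374 | 1,401 |

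The plan assumed 900.

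If the recalculation uses 0.3 × the control rate as a difference margin, the noncentrality of the log-RR test is log(1.3)/0.30 = 0.875 times the one computed, whatever the control rate. A reported 80% then means:
- both at 0.025: 2.802 × 0.875 − 1.960 = 0.491, power 69%;
- both at 0.05: 2.486 × 0.875 − 1.645 = 0.530, power 70%;
- computed at 0.025, tested at 0.05: 2.802 × 0.875 − 1.645 = 0.806, power 79%.

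**Step 7: the synopsis.** A 1-point margin at 0.025 needs 7.849 × 2 × 0.0291 / 0.01² × 2.798/900 = 14.20 clusters, or 15.20 with one added. That is 15 to 16 clusters, not 19.

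**The case against.** The strongest reply is that 19 is not a slip of arithmetic. SAP 3.3 itself converts the margin to 0.9 points, and 19 reproduces for that margin at 0.025. That stands: the fault is a mismatch between the sizing scale and the test scale. The match in Step 2 uses one added cluster and the match in Step 4 does not, and with the same addition the latter would round up to 20. So 19 cannot be traced with certainty to either route.

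A second reply is that SAP 6.2 pairs the ratio test with a one-sided 95% interval, where power with the 20 planned clusters is adequate. Moreover, SAP 3.4 read literally (margin re-derived as a difference, alpha left at 0.025) followed by the SAP 6.2 test gives 79%, so the two discrepancies nearly cancel. The figure is right, but the cancellation is accidental and depends on taking 0.05 as the test level, which contradicts SAP 3.3. Protocol 10.3, read conventionally as two-sided, agrees with 0.025, which leaves the SAP 6.2 sentence as the outlier.

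A third reply concerns the assumptions. At 0.025 with 20 × 900, power reaches 80% if the true risk ratio is about 0.97–0.98 or the ICC about 0.0015–0.0016, and adjustment for stratification factors may help. This is fair, and the power figures are conditional on the assumptions. It works in both directions, however: at ICC 0.003 power falls to 62% at 0.025 and 74% at 0.05. If 900 is the number enrolled and 10% are lost (810 analysed), power with 20 clusters is 71–73% and 81–82%.

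None of these replies gives a reading in which the sections agree on both alpha and scale.

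**Conclusion.** The concern holds. As written, "To have 80% power to detect a risk ratio 1.3" at one-sided 0.025 is not met by the SAP 6.2 test. Power is about 70–72% with 19 clusters per arm and 72–74% with 20, and 80% needs 23–24 clusters, or 24–25 with a t reference. A truly equivalent intervention would then fail the gate about 26–28% of the time, against the 20% implied. If 0.05 is the intended level, power is adequate (82–83% with 20 clusters), but the chance of a false non-inferiority claim is twice that stated in SAP 3.3. The reading chosen also moves the SAP 3.4 trigger from roughly 650–690 to about 1,400 evaluable children per facility, at 20 facilities per arm and 3% failure.

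These figures rest on the documents' failure rate, ICC and cluster size, and on the assumptions of a true risk ratio of 1, equal clusters and no gain from adjustment. The conflict between the two alphas rests on none of these and can be read directly from the text.

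**What to change.** 1. Settle one alpha for the non-inferiority test and state it identically in SAP 3.3, SAP 6.2 and protocol 10.1.1 and 10.3, with the matching confidence level.
2. Give the sample-size formula and restate power on the risk-ratio scale at that alpha: about 72–74% for 20 × 900 if 0.025 is kept, about 82–83% if 0.05 is chosen.
3. In SAP 3.4, say that the 80% trigger refers to power for the risk-ratio test at that alpha, computed from the observed number of children with a day-7 outcome. Show a range of ICC values as a sensitivity check.
4. Replace the 1-point margin in the protocol synopsis with the risk ratio of 1.3.

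The cost is wording plus one calculation by the independent statistician whom SAP 3.4 already assigns. Keeping 0.025 means stating a less favourable power, and SAP 3.4 may then call for longer enrolment or more facilities. Choosing 0.05 means stating the looser error rate openly.
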